# 8.7.3. Rate of Investigator-Confirmed HAE Attacks during Dosing in the Effective Treatment Period

The rate of investigator-confirmed HAE attacks during dosing in the effective treatment period is a secondary endpoint for Part 1.

Summaries and analysis of the investigator-confirmed attack rate using the ITT population for the effective treatment period (Day 8 through Week 24, inclusive) will be conducted using Poisson regression, similar to what is done for the primary efficacy endpoint analysis.

Summary displays will be updated at the end of Part 2 to include data collected during Part 2 of the study. For subjects originally randomized to placebo, data on active treatment will be summarized using the adjusted visits.

# 8.7.4. Use of HAE Attack Medications

The use of HAE attack medications over 24 weeks is an exploratory efficacy endpoint for Part 1 and a secondary endpoint for Parts 2 and 3. Use of HAE medications based on diary data will be summarized separately from concomitant medications. In addition, summaries and analyses of the rate of investigator-confirmed HAE attacks requiring treatment will be provided for Part 1 and for the study period from Day 1 to the end of Part 2. The analysis will be performed similarly to the analysis of rate of confirmed HAE attacks. For a list of medications that qualify as targeted and non-targeted HAE attack medications, see Section 6.7.5.7. Separate summaries of HAE attack medication use for Part 3 will be produced based on adjusted subject-reported attacks.

A Kaplan-Meier plot of time to first use of a targeted HAE rescue medication to treat an investigator-confirmed attack and corresponding summary table will be produced for Part 1.

## 8.7.5. Discontinuations due to Lack of Efficacy

Discontinuation due to lack of efficacy is a secondary endpoint for Parts 2 and 3.

A summary of the number of subjects who discontinue due to lack of efficacy will be provided with subject disposition. The summary will include the number and percent of subjects who discontinue due to lack of efficacy during Part 1, 2 and 3 as well as overall.

# 8.8. Analysis of Additional Exploratory Efficacy Endpoints

### 8.8.1. Number and Proportion of Subjects with No Attacks

The number and proportion of subjects with no attacks over 24 weeks is an exploratory endpoint for Part 1. This information will be descriptively summarized. The summary will be repeated at the end of Part 2 as a summary of the number and proportion of subjects with no attacks over the entire dosing period of 48 weeks for those originally randomized to active treatment. A summary of 24-Week data at the end of Part 2 will be conducted including subjects originally randomized to placebo. The summary will show the number and proportion of subjects with no attacks during the first 24 weeks of active treatment, whether received in Part 1 or Part 2 and separately for those who started active treatment in Part 2. Subjects who discontinue treatment prior to the end of the reporting period of interest will not be considered attack-free. A separate summary of the number and proportion of subjects in Part 3 will be provided.

For Part 1, a chi-squared test will be used to test whether there is a difference in the proportion of subjects with no attacks comparing each active dose to placebo. For the chi-squared analysis, if the expected number of subjects in any individual cell is < 5, Fisher's exact test will be used instead the chi-squared test.

A Kaplan-Meier plot and corresponding summary of time to first attack will be produced for Part 1 for both the entire dosing period and the effective dosing period (Day 8 to Week 24).

## 8.8.2. Proportion of Responders to Study Drug.

Subjects will be classified as responders or non-responders for Part 1 as discussed in Section 6.7.5.4. A responder is defined as a subject who has at least a 50% relative reduction in the rate of investigator-confirmed HAE attacks meeting the stricter screening criteria during treatment compared with the baseline attack rate. A summary of the number and proportion of responders by study treatment will be produced. Logistic regression with responder status as the outcome variable and treatment and baseline attack rate as independent variables in the model will be used to compare each active treatment to placebo treatment. Point estimates of the odds ratios for response comparing 110 mg to placebo and 150 mg to placebo will be calculated along with corresponding 95% CIs. If the proportion of responders is near zero for the placebo treatment (or for either active treatment), logistic regression may not be an appropriate methodology for analysis and Fisher's exact test will be used in place of logistic regression.

### 8.8.3. Attack Characteristics

Characteristics of attacks including location of attack, duration of attacks from start to finish and from start to the time the worst symptoms of the attack were over, time since last dose, triggers, swelling, other symptoms, whether the attack was treated, severity as assessed by the subject and by the investigator, ability to do daily activities, appearance affected, professional care sought, and location of professional care will be summarized and listed.

A summary of duration of attack for abdominal, peripheral and mixed attacks will also be provided.

# 8.9. Summary of Reasons for Efficacy Non-Evaluability/Exclusion from Efficacy Analyses

A listing of subjects excluded from the PP population will be provided along with reason for exclusion.

# 9. HEALTH OUTCOMES

# 9.1. EQ-5D-5L

EQ-5D-5L is a health outcomes endpoint for Part 1 and a secondary endpoint for Parts 2 and 3. The 5-digit numbers representing the health state of each subject will be listed along with the VAS score and computed index value (Section 6.7.6.1). The VAS score and computed EQ-5D-5L index value will be summarized descriptively for Part 1 and for the entire study period.

Note that this study uses the questionnaire in its validated form for subjects to report their health status "*today*". If the subject has had an HAE attack since the last visit, starting at Week 4, the subject completes the questionnaire a second time to reflect back on health status during a "*usual attack*". On summary tables, the "*today*" and "*usual attack*" questionnaire results will appear in different rows and analyses should be separated.

For Part 1, MMRM will be used to compare each active dose to placebo for each time point. For this analysis, either the change from baseline VAS score or EQ-5D-5L index value using the "*today*" questionnaire will be included as the dependent variable in the model with fixed effects for treatment, baseline attack value, baseline VAS or EQ-5D-5L index score as appropriate, visit, visit by treatment interaction, and a random effect for subject included as independent variables. An unstructured covariance structure will be used.

Analyses at the end of the study will be descriptive and will cover the entire study period.

For Part 1 and entire study period analyses, categorical summaries by treatment group and visit will be provided for responses to each individual question. In addition, summaries of VAS and index scores during a *"usual attack"* will be provided.

Plots of VAS and EQ-5D-5L index mean scores over time and change from baseline mean scores will be provided for Part 1 analysis and for the analysis at end of the study using the health status *"today"*. For Parts 2 and 3, plots of mean scores over time by treatment will be shown separately for active treatment for the subjects originally randomized to placebo.

# 9.2. Treatment Satisfaction Questionnaire for Medication

TSQM is a health outcomes endpoint for Part 1 and a secondary endpoint for Parts 2 and 3. TSQM is measured at baseline.

TSQM scores for Effectiveness, Side Effects, Convenience, and Global Satisfaction will be calculated for each visit as discussed in Section 6.7.6.2. The TSQM scores will be summarized by score, treatment, and visit with separate summaries for Part 1 and for the entire study period. For Part 1, MMRM will be used to compare each active dose to placebo for each time point. For this analysis, the TSQM change from baseline score of interest will be included as the dependent variable in the model with fixed effects for treatment, baseline attack value, baseline TSQM

score, visit, visit by treatment interaction and a random effect for subject included as independent variables. An unstructured covariance structure will be used.

Separate figures of Effectiveness, Side Effects, Convenience, and Global Satisfaction mean scores over time with 1 line per treatment group will be provided. There will be 1 set of figures for Part 1 and another for the entire study period. For the analysis at the end of the study, the figure will have separate lines for active treatment for subjects originally randomized to placebo, showing mean scores over time by treatment.

In addition, categorical summaries by treatment group and visit will be provided for responses to each individual question.

# 9.3. Work Productivity and Activity Impairment

WPAI is a health outcomes endpoint for Part 1 and a secondary endpoint for Parts 2 and 3. Absenteeism, presenteeism, work productivity loss, and activity impairment will be calculated as described in Section 6.7.6.3. WPAI scores will be summarized descriptively by treatment group and visit for Part 1 and for the entire study period. For Part 1, MMRM will be used to compare each active dose to placebo for each time point. For this analysis, the change from baseline WPAI score of interest will be included as the dependent variable in the model with fixed effects for treatment, baseline attack value, baseline WPAI score, visit, visit by treatment interaction and a random effect for subject included as independent variables. An unstructured covariance structure will be used.

In addition, summaries statistics by treatment group and visit will be provided for responses to each individual question (Q2 to Q6) with a categorical summary provided for Q1.

Separate figures of each of the WPAI mean scores and change from baseline mean scores over time with 1 line per treatment group will be provided. There will be 1 set of figures for Part 1 and another for the entire study period. For the plots produced at the end of the study, the figure will have separate lines for active treatment for subjects originally randomized to placebo.

# **10. SAFETY AND TOLERABILITY**

Analyses of safety and tolerability will be conducted at the end of Part 1 of the study and repeated for the entire study period.

# 10.1. Adverse Event Preferred Term and System Organ Class Summary Tables

The following are Part 1 secondary endpoints and Part 2 and 3 primary endpoints:

- Number and proportion of subjects with a TEAE
- Number and proportion of subjects who discontinue due to a TEAE
- Number and proportion of subjects who experience a TESAE
- Number and proportion of subjects who experience a Grade 3 or 4 TEAE

AEs will be mapped to the MedDRA version 19.1 PT and system organ class (SOC). AEs are assessed by the Investigator as Grade 1 (mild), Grade 2 (moderate), Grade 3 (severe), or Grade 4 (life-threatening) according to Division of Microbiology and Infectious Diseases (DMID) using the November 2007 criteria. If a subject experiences multiple events that map to a single PT, the greatest severity grade according to the DMID criteria and strongest investigator assessment of relation to study medication will be assigned to the PT for the appropriate summaries. All AEs will be listed for individual subjects showing both verbatim and preferred terms.

TEAEs are defined as AEs that occurred on or after first dose of study treatment, whether in Part 1, 2 or 3, and will be assigned to the relevant treatment depending on when the TEAE began (Part 1 or Part 2 and 3 treatment). AEs occurring 30 days after the last dose for subjects who discontinue study treatment in Part 1 or up to 30 days after last dose in Part 2 or 3 will be considered as TEAEs and will be associated with Part 1, 2 or 3 respectively. Note that Investigators are not required to contact subjects after the last follow-up if it occurs prior to 30 days from last dose. All AEs that occurred prior to the initiation of study treatment or those recorded more than 30 days after the last dose of study treatment will be excluded from the tables but will be included in the listings.

Drug-related events are defined as those AEs that the Investigator believes were possibly, probably, or definitely related to the study drug.

### 10.1.1. Summaries of Adverse Event Incidence Rates for All Subjects and Incidence Rates for Serious Adverse Events, Discontinuations due to Adverse Events, and Deaths

A brief summary of TEAEs will show, by treatment group, the number and percentage of subjects who 1) had any TEAE, 2) had any drug-related event, 3) permanently discontinued from study drug due to an TEAE, 4) had any serious adverse event (SAE), 5) had any Grade 3 or higher TEAE, 6) had any Grade 3 or higher drug-related TEAE, 7) had any TEAE leading to interruption of study drug, 8) had a drug-related SAE, or 9) had a fatal SAE.

TEAEs will be summarized by treatment group. For each SOC and PT, the number and percentage of subjects reporting an event will be calculated. In summary tables, SOCs and events within a SOC will be presented by decreasing frequency count based on the total number of events. Multiple events (by subject or SOC as appropriate) will be counted only once per subject per dose in each summary. For summaries that use severity grade, the most severe event will be selected.

The following summary tables (number and percentage of subjects) of TEAEs (by SOC and PT) will be provided by treatment group:

- Overall summary of TEAEs
- Summary of TEAEs
- Summary of drug-related TEAEs
- Summary of TEAEs by severity
- Summary of treatment-emergent Grade 3 or Grade 4 AEs
- Summary of drug-related, treatment-emergent Grade 3 or Grade 4 AEs

### 70

# CONFIDENTIAL

- Summary of TESAEs
- Summary of TEAEs leading to permanent discontinuation of study treatment
- Summary of TEAEs leading to interruption of study treatment
- Summary of drug-related TESAEs

In addition, a summary of frequent TEAEs will be provided by PT (not by SOC and PT), in decreasing order of frequency. Frequent TEAEs will be defined as events that occur in at least 5% of the total number of subjects in the clinical trial.

A summary of TEAEs by age group will also be provided

Data listings will be provided for all AE data. In addition to listing all AEs, distinct data listings will also be provided for the following:

- Grade 3 or Grade 4 AEs
- AEs leading to permanent study discontinuation
- SAEs (fatal and non-fatal)

A forest plot of most-frequent treatment-emergent AEs sorted by relative risk will be produced using the format recommended by the FDA/Industry/Academia Safety Graphics working group (https://www.ctspedia.org/do/view/CTSpedia/StatGraphHome). The format of the plot to be used is the example plot of most-frequent on-therapy AEs sorted by risk difference. However, the relative risk (aka risk ratio) will be displayed rather than the risk difference. The 95% confidence interval for the relative risk will be derived using the assumption of normality of the log of the relative risk.

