#### Part 1 (24-week evaluation of blinded efficacy and safety)

Subjects with HAE Type 1 or 2 will be eligible for the study following assessment of data obtained from screening procedures, including demonstration of a minimum number of attacks documented during a prospective run-in period of 2 to 8 weeks from the date of the screening visit.

Treatment-eligible subjects will receive study drug (BCX7353 or placebo) in Part 1 of the study based on randomization in a 1:1:1 ratio into 1 of 3 treatment groups:

- Group 1: BCX7353 110 mg administered orally QD for 24 weeks
- Group 2: BCX7353 150 mg administered orally QD for 24 weeks
- Group 3: Placebo administered orally QD for 24 weeks

Enrollment into treatment groups will be stratified by the baseline HAE attack rate ( $\geq 2$  attacks/month vs. < 2 attacks/month).

Details of acute attacks of angioedema will be recorded in an electronic diary (e-diary). Attacks will be treated in accordance with the subject's normal standard of care. Treatment medications for angioedema attacks will not be provided by the Sponsor.

Within approximately 2 business days of the end of each attack that occurs beginning at the screening visit through the follow-up visit after Part 2, subjects will be contacted by the Investigator to discuss the clinical characteristics of the attack, any questions the Investigator has on the entered data or to gain additional attack details not included in the e-diary that the Investigator deems important to clinically evaluate the event, as applicable. This information, in conjunction with the e-diary record, will be used by the Investigator to verify or reject the event recorded in the diary as an HAE attack. All Investigator-confirmed attacks of HAE must include symptoms of swelling; prodromal symptoms in the absence of swelling are not considered HAE attacks, regardless of treatment. Symptoms of swelling, in addition to visible swelling, may also include symptoms in the oropharyngeal or abdominal regions that are indicative of internal swelling.

The main study will be comprised of adult subjects ( $\geq 18$  years of age); a substudy in participating regions will allow adolescent subjects  $\geq 12$  to 17 years of age to participate. Main study and substudy subjects will be randomized via a separate randomization scheme; however, study-mandated procedures will be identical, and analyses will include all subjects who participate in the study.

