#### Number of Subjects (planned and analyzed):

Approximately 120 subjects will be enrolled in this study (n = 40 per Part 1 dose group). This includes any adolescent subjects enrolled in the substudy.

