14.2.3.3.ES	ITT	Plot of Mean AE-QoL Scores Over Time, Entire Study		
14.2.3.4	ITT	Plot of Mean Change from Baseline AE-QoL Scores Over Time, Part 1		
14.2.3.4.ES	ITT	Plot of Mean Change from Baseline AE-QoL Scores Over Time, Entire Study		
14.2.3.5	ITT	Cumulative Distribution of Total AE-QoL Change from Baseline at Week 24		
14.2.3.6	ITT	Forest Plot of Results of Subgroup Analyses of Total AE-QOL Change from Baseline at Week 24, Part 1		
14.2.8.2	ITT	Kaplan-Meier Plot of Time to First Investigator-Confirmed Attack, Part 1		
14.2.9.2	ITT	Kaplan-Meier Plot of Time to First Use of Targeted HAE Rescue Medication to Treat an Investigator-Confirmed Attack, Part 1		
14.3.1.13	ITT	Forest Plot of Treatment-Emergent Adverse Events Sorted by Relative Risk, Part 1		
14.3.1.13.ES	ITT	Forest Plot of Treatment-Emergent Adverse Events Sorted by Relative Risk, Entire Study		
14.3.1.26	Safety	Kaplan-Meier Plot of Time to Development of Investigator-identified Rash, Part 1		
14.3.1.26.ES	Safety	Kaplan-Meier Plot of Time to Development of Investigator-identified Rash, Entire Study		
14.3.1.28	Safety	Kaplan-Meier Plot of Duration of Investigator-identified Rash, Part 1		
14.3.1.28.ES	Safety	Kaplan-Meier Plot of Duration of Investigator-identified Rash, Entire Study		
14.3.1.40	Safety	Kaplan-Meier Plot of Time to First Occurrence of a GI Abdominal-related Adverse Event Part 1		
14.3.1.40.ES	Safety	Kaplan-Meier Plot of Time to First Occurrence of a GI Abdominal-related Adverse Event Entire Study		
14.3.1.42	Safety	Kaplan-Meier Plot of Duration of GI Abdominal-related Adverse Events Part 1		
14.3.1.42.ES	Safety	Kaplan-Meier Plot of Duration of GI Abdominal-related Adverse Events Entire Study		
14.3.1.43	Safety	Plot of Occurrence of Treatment-Emergent GI Abdominal-related Adverse Events, Part 1		
14.3.1.43.ES	Safety	Plot of Occurrence of Treatment-Emergent GI Abdominal-related Adverse Events, Entire Study		
14.3.5.20	Safety	Plot of Liver Function Test Profiles for Subjects with Grade 3 or 4 Liver Abnormalities, Part 1		
14.3.5.21	Safety	Hy's Law Plot of Maximum Total Bilirubin vs. Maximum ALT, Part 1		

Output #	Population Title	Output Title		
14.3.5.21.ES	Safety	Hy's Law Plot of Maximum Total Bilirubin vs. Maximum ALT, Entire Study		
14.3.5.22	Safety	Liver Test Safety Panel Over Time, Baseline vs. On-Study, Part 1		
14.3.5.22.ES	Safety	Liver Test Safety Panel Over Time, Baseline vs. On-Study, Entire Study		

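### The adverse-event forest plot takes its interval from the log relative risk, which does not exist when an arm has no events, and the SAP gives no rule for that case.

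*SAP*

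**What the plan says.** The point concerns only the SAP, which is for study BCX7353-302. The protocol supplied is for study BCX7353-202 and has no such plot.

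- SAP 10.1.1: "A forest plot of most-frequent treatment-emergent AEs sorted by relative risk will be produced".
- The layout comes from a published example: "The format of the plot to be used is the example plot of most-frequent on-therapy AEs sorted by risk difference". The SAP then changes the measure on purpose: "However, the relative risk (aka risk ratio) will be displayed rather than the risk difference".
- The interval: "The 95% confidence interval for the relative risk will be derived using the assumption of normality of the log of the relative risk".
- The frequency rule, earlier in the same section: "Frequent TEAEs will be defined as events that occur in at least 5% of the total number of subjects in the clinical trial". It pools the arms, so no placebo event is needed.
- Size: "Approximately 120 subjects will be enrolled in this study (n = 40 per Part 1 dose group" (Technical Summary Report), with "randomization in a 1:1:1 ratio into 1 of 3 treatment groups". That is about 80 subjects on active drug and 40 on placebo.
- SAP 17.1, Figures: output 14.3.1.13 is "Forest Plot of Treatment-Emergent Adverse Events Sorted by Relative Risk, Part 1", and 14.3.1.13.ES is the entire-study version. Both are assigned to the ITT population. SAP 6.5.2 names the safety population for safety data.

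The SAP does provide for sparse data in two efficacy analyses. Fisher's exact test replaces the chi-squared test for attack-free subjects when an expected count is below 5 (8.8.1). It replaces logistic regression for responders when a response proportion is near zero (8.8.2). Section 10.1.1 has no counterpart.

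**The concern.** A Wald interval on the log scale needs at least one event in each arm. With about 40 subjects on placebo, a term can be common enough on drug to be plotted and still have no placebo case. The stated method then yields neither a finite estimate nor an interval. Such terms cannot be ordered among themselves, because each has an infinite relative risk. The mirror case, no events on active drug, gives a relative risk of 0 and an equally undefined log.

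At stake is whether the figure can be produced as specified. With no rule in the SAP, someone must choose one when the zeros appear, possibly after unblinding. The choice matters, because continuity corrections of different size give very different points and limits for the same counts.

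**Working it through.** **1. Arm size.** SAP 4.3.1 gives 32 per group for 94% power (difference 0.5, SD 0.55, two-sided 0.05), raised for 20% dropout. The two-sample t calculation gives 0.947 and the normal approximation 0.953, so the stated power is reproduced. 32/(1 − 0.20) = 40 per group, as stated.

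**2. Frequency threshold.** 0.05 × 120 = 6 subjects, from any arm.

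**3. The stated interval.** With a events of n1 on drug and b of n2 on placebo:

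RR = (a/n1)/(b/n2), 95% CI = exp{ log RR ± 1.96 × √(1/a − 1/n1 + 1/b − 1/n2) }.

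- 6/40 vs 5/40: RR = 1.20, SE = √(1/6 − 1/40 + 1/5 − 1/40) = 0.563, CI 0.40 to 3.62. This row plots.
- 6/80 vs 0/40, which just meets the threshold: RR = 0.075/0 and the SE contains 1/0. There is no interval.
- 12/80 vs 0/40: the same. The two zero-placebo rows tie, although their risk differences are 7.5 and 15.0 points.

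**4. How often a plotted term would have no placebo event.** No document gives adverse-event rates for this population, so the rates here are assumptions. Let A ~ Bin(80, 0.10) and B ~ Bin(40, p). Then

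P(B = 0 | A + B ≥ 6) = P(A ≥ 6) × (1 − p)^40 / P(A + B ≥ 6), with P(A ≥ 6) = 0.823.

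| Placebo rate p | (1 − p)^40 | P(A + B ≥ 6) | P(no placebo event, given plotted) |
|---|---|---|---|
| 1% | 0.669 | 0.856 | 64% |
| 2% | 0.446 | 0.884 | 42% |
| 3% | 0.296 | 0.907 | 27% |
| 5% | 0.129 | 0.941 | 11% |
| 10% | 0.015 | 0.984 | 1% |

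With a 5% rate in both arms the same calculation gives 5%.

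**5. An unplanned repair is not neutral.** For 6/80 vs 0/40, adding a constant to each cell gives:

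| Constant | RR | 95% CI |
|---|---|---|
| 0.5 | 6.58 | 0.38 to 114 |
| 0.25 | 12.6 | 0.24 to 673 |
| 0.1 | 30.6 | 0.06 to 15,637 |

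**6. Intervals that exist, for 6/40 vs 0/40.**

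- *Miettinen-Nurminen score interval for RR.* Solve (a/n1 − R·b/n2)² = 1.96² × V(R), where V(R) = [p̃1(1 − p̃1)/40 + R²·p̃0(1 − p̃0)/40] × 80/79 and p̃1 = R·p̃0 are the maximum-likelihood estimates under ratio R. At R = 1.64, p̃0 = 0.058, p̃1 = 0.095 and V = 0.00586, so 0.0225/0.00586 = 3.84 = 1.96². The lower limit is about 1.6 and the upper end is open.
- *Newcombe interval for the risk difference.* The Wilson limits are 0.0706 to 0.2907 for 6/40 and 0 to 0.0876 for 0/40. Lower: 0.15 − √[(0.15 − 0.0706)² + 0.0876²] = 0.032. Upper: 0.15 + (0.2907 − 0.15) = 0.291. The result is 15.0%, 3.2% to 29.1%.

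**7. Population.** SAP 6.5.3 puts all randomized subjects in ITT, dosed or not, and analyses them as randomized. SAP 6.5.2 requires at least one capsule and analyses by treatment received. The neighbouring adverse-event figures for rash and gastrointestinal events in 17.1 are assigned to Safety.

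**The case against.** The strongest reply is that little is lost. Section 10.1.1 requires counts and percentages by treatment group for every preferred term, plus a table of frequent events. Section 10.1.2 adds summaries and Kaplan-Meier displays for rash and gastrointestinal events. Safety analysis is described as mainly descriptive, and no decision rests on the figure. This stands, and it limits the point to the figure.

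A reader might go further and infer that the plot leaves out the clearest harms and so makes the drug look safer than the counts show. The documents do not support that. Nothing in the SAP says rows with a zero are dropped, and an infinite relative risk ranks naturally above every finite one. Nor are zero-placebo rows always the strongest signals. The threshold case of 6/80 vs 0/40 has a risk difference of 7.5 points (Newcombe −2.1 to 15.4) and Fisher p = 0.18. A row of 12/40 vs 1/40 (p = 0.001) plots normally.

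A reader might also infer that choosing relative risk is itself the error. It is a stated, deliberate choice. Replacing it with the risk difference is a trade-off, and the defect needs only an interval that survives zero cells.

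Finally, the figure shells are kept in a separate document (SAP 17.1) and might hold a display convention. That could settle where a row is drawn, but it cannot supply an interval that the stated method does not define. SAP 6.4 treats format changes as needing no revision but true changes of analysis method as needing documentation, so the interval belongs in the SAP.

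**Conclusion.** The concern holds as a contained defect. The specified interval does not exist when either compared arm has no events, data of that kind can meet the frequency rule, and the SAP has no fallback. For an event with a 10% rate on drug, the chance that a plotted row is affected runs from 64% at a 1% placebo rate to 1% at a 10% placebo rate. It matters for events rare on placebo and hardly at all for common ones. Affected rows lack an interval and tie with one another. They are not lost from reporting, and the plan does not support a claim that the figure would understate harm.

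The conclusion rests on these readings:

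- Placebo is the comparator. Section 10.1.1 does not say so, nor whether each dose or the pooled active group is compared.
- The plot uses the 5% definition, which the text does not expressly tie to it.
- Total size is about 120. SAP 4.1 and 4.4.1 still give 96, where 0.05 × 96 = 4.8, so 5 subjects qualify and the conclusion is unchanged.

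The percentages apply to Part 1. The missing rule applies to both versions of the figure. The ITT label is a separate, smaller inconsistency. It can alter denominators and the arm of any subject given the wrong treatment, but undosed subjects cannot have a treatment-emergent event.

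**What to change.** In SAP 10.1.1, replace the log-normal interval with one defined for zero cells. Either of these serves:

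- Keep relative risk with a Miettinen-Nurminen score interval, drawn with an open upper end when placebo has no events.
- Return to the risk difference of the referenced template, with a Newcombe or score interval.

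If relative risk is kept, place zero-placebo terms at the top of the sort, ordered among themselves by risk difference. Name the arms being compared and print the counts on each row. In SAP 17.1, change figures 14.3.1.13 and 14.3.1.13.ES from ITT to the safety population.

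The cost is a few words of SAP text, two population labels and an edit to the figure program. The drawback is some open-ended bars or, with the risk difference, small absolute differences for rare events.
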